## Protocol

**Protocol:**

Temporomandibular disorders (TMD) are musculoskeletal disorders that are commonly encountered, with pain in the temporomandibular joint (TMJ) and jaw closing muscles. Pain that involves the temporomandibular joint includes inflammatory pathologies such as arthritis, painful disk displacements and many times have an overlay of psychosocial comorbidities due to the uncontrolled pain. TMJ osteoarthritis is an intracapsular condition affecting the temporomandibular joint and presents with remodeling of the TMJ articulating tissues including the condyle and articular eminence secondary to inflammation resulting in intracapsular pain. There is a paucity of information regarding the relative effectiveness of different therapies for the treatment of patients with TMJ osteoarthritis. The identification of the least invasive and most efficacious therapy is vital to proper management of these patients with temporomandibular joint pain and disability. The purpose of this study is to establish the relative efficacy of TMJ arthrocentesis with steroid supplementation (a known effective therapy) compared to TMJ arthrocentesis with a supplement of plasma rich in growth factors (PRGF) for patients with TMJ osteoarthritis. Plasma rich in growth factors is isolated from the patient's own blood and injected into the temporomandibular joint to activate stem cells that may restore some of the articulating tissues that were lost during degeneration changes within the joint secondary to osteoarthritis. Pain and disability will be assessed using standard pain and physical measures that are recorded before and after treatment. Patients enrolled into the study will be examined and treated at the Department of Oral and Maxillofacial Surgery Faculty/Resident clinic. At the first appointment, they will be examined following standard procedures (medical history, physical exam, imaging by cone beam computerized tomography (CBCT)) to determine their diagnosis(es) and if they would potentially benefit from the TMJ arthrocentesis procedure. If the patient meets the inclusion criteria for the study and with their informed consent on the day of their TMJ arthrocentesis procedure, they will be required to have a pregnancy test if below age 60 and complete a questionnaire about their physical and pain symptoms and undergo a standardized clinical exam. The patients will then undergo the standard clinical protocol for TMJ arthrocentesis followed by either a 2 cc steroid/bupivacaine hydrochloride supplementation (standard treatment group) or a 2 cc PRGF supplementation (experimental group) into the TMJ. Follow-up appointments will be conducted at 1 month, 3 months and 6 months when the pain VAS measures and a clinical exam will be assessed. If patients have not experienced improvement in their primary outcome measure (TMJ pain) at the 3 month evaluation, the patient will have a second TMJ arthrocentesis procedure that will be supplemented with the alternative medication/growth factors (steroid or PRGF) using a cross-over design. Data from these patients will be analyzed separately from patients that complete the six month study. Also at 6 months, a second CBCT image of the temporomandibular joints will be obtained to determine the extent of bone remodeling within the TMJ. The results of this study should provide new information on the efficacy of PRGF supplementation for management of temporomandibular joint osteoarthritis.

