Clinical Trial Number: NCT04731233

Title: A Randomized, Double-Blind Study of the Efficacy of Platelet-Rich Growth Factor (PRGF) Supplementation Compared to Steroid Supplementation After Temporomandibular Joint (TMJ) Arthrocentesis in Female Patients With TMJ Osteoarthritis (OA)

Date: January 2, 2025

Proposed Statistical Analyses

Statistical Analyses

Statistical analyses will consist of descriptive statistics (mean, standard deviation for parametric data; median and range for non-parametric data) and inferential statistics (two way ANOVA, 1 between (treatment groups), 1 within (time)) using a probability level of < 0.05). The primary outcome variable will be intracapsular pain.

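### The SAP does not say which term of the group-by-time ANOVA decides efficacy, and the protocol separates patients from the 6-month analysis according to their own 3-month pain

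*SAP*

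**What the plan says.** The SAP (Statistical Analyses) gives one inferential method, a "two way ANOVA, 1 between (treatment groups), 1 within (time)) using a probability level of < 0.05". On the outcome it adds: "The primary outcome variable will be intracapsular pain". It attaches no visit, no summary measure and no deciding term to that outcome.

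The protocol records pain before treatment as well as afterwards. On the later visits it says: "Follow-up appointments will be conducted at 1 month, 3 months and 6 months when the pain VAS measures" are taken. It makes none of these visits primary for pain. The condition for a second procedure is worded: "If patients have not experienced improvement in their primary outcome measure (TMJ pain) at the 3 month evaluation". What follows for those who meet it is that "the patient will have a second TMJ arthrocentesis procedure that will be supplemented with the alternative medication/growth factors (steroid or PRGF"). On the analysis of this group the protocol says: "Data from these patients will be analyzed separately from patients that complete the six month study". The SAP does not mention the second procedure or the separate analysis.

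**The concern.** The trial is meant to establish relative efficacy, which calls for one between-arm difference fixed in advance. Two features of the plan stand in the way.

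- **The deciding test is open.** The group term and the interaction answer different questions, and the answer from each depends on whether baseline counts as a level of time. That choice could be made after the data are in.
- **The analysed set depends on the outcome.** If patients who have a second procedure are analysed separately, the remaining 6-month comparison covers only those who had improved by 3 months. If treatments differ, the weaker arm loses more patients and keeps its better responders, which tends to hide the difference. If those patients stayed in their original arm instead, the 6-month comparison would be as randomised, but some patients would by then have had both supplements.

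**Working it through.** The documents give no sample size, SD, effect size or power, so there is no planned figure to reproduce. The only numerical inputs from the documents are the 0.05 level, two arms, and follow-up at 1, 3 and 6 months with a pre-treatment measurement. Everything else below is assumed: normal scores with SD 1, a true difference of d = 0.6 SD, n = 30 per arm where power is shown, and between-visit correlation r of 0.3, 0.5 or 0.7. Correlation is equal for all pairs of visits (compound symmetry) unless AR(1) is stated.

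**1. What each ANOVA term estimates.** Take an effect that is constant after treatment.
- Baseline as a level: the effects are (0, d, d, d). The group term averages them: (0 + d + d + d)/4 = 0.75d.
- The interaction then has (4 - 1)(2 - 1) = 3 degrees of freedom. It tests whether the difference varies over time and yields no single difference.
- These two facts do not depend on the assumed n or r.

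**2. Power of the readings (r = 0.3 / 0.5 / 0.7).**
- Group term, baseline as a level: noncentrality 0.75d / sqrt[((1+3r)/4)(2/n)]. At r = 0.3 this is 0.45 / sqrt(0.475 × 0.0667) = 2.53. Power 0.70 / 0.58 / 0.49.
- Interaction, baseline as a level: lambda = (n/2) Σ(e - mean e)² / (1 - r), with Σ(e - mean e)² = 0.75d² = 0.27. At r = 0.3 this is 15 × 0.27 / 0.7 = 5.79. Power 0.49 / 0.65 / 0.88.
- Group term, follow-ups only: noncentrality d / sqrt[((1+2r)/3)(2/n)]. Power 0.88 / 0.80 / 0.72.
- Baseline-adjusted 3-month difference: noncentrality d / sqrt[(1-r²)(2/n)(1+1/(2n-4))]. Power 0.66 / 0.74 / 0.89.
- Baseline-adjusted mean of 1 and 3 months: replace (1-r²) by ((1+r)/2 - r²). Power 0.86 / 0.89 / 0.97. If the 1-month effect is half the 3-month effect, the mean effect is 0.75d and power is 0.62 / 0.67 / 0.81.

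The ANOVA powers assume that no patient is left out and none has a second procedure, so they favour the ANOVA.

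**3. Type I error.**
- One named test: 5%.
- Either test accepted: 1 - 0.95² = 0.0975. Simulation of the four-level ANOVA under the null (20,000 runs, 30 per arm) gives 0.098-0.103.
- Each test at 0.025: 1 - 0.975² = 0.0494 if the two tests are independent. Under AR(1) correlation of 0.5 or 0.7 without correction, simulation gives 0.056 and 0.063.

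**4. Leaving out 3-month non-improvers.** The protocol does not define improvement. Here non-improvement is taken as a 3-month score not below baseline, with mean improvement of 0.5 or 1.0 SD in the weaker arm and a true difference of 0.60 SD (simulation, 1,000,000 per arm).
- Share removed, compound symmetry: about 10-34% of the weaker arm and 2-18% of the other.
- Baseline-adjusted 6-month difference: about 0.52-0.57 SD under compound symmetry, about 0.45-0.53 SD under AR(1) 0.5-0.7.
- Baseline-adjusted 3-month difference, if the same patients are also left out at that visit: about 0.38-0.50 SD under compound symmetry.
- With no true difference, the exclusion produces no bias in this model.

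**The case against.** A repeated-measures ANOVA uses all visits by design, so not naming a single visit is not in itself an error. Stating the deciding term and the levels of time would close the first gap without moving the primary comparison to 3 months. The protocol's wording about measurement before and after treatment also leans towards baseline being a level. With baseline in and r = 0.5, the two terms have similar power (0.58 and 0.65). This stands as far as it goes, but it leaves the outcome-dependent exclusion untouched. That exclusion is what makes the plan worse than an available alternative, not merely less detailed. The protocol's 3-month reference to the primary outcome does not fill the gap either: it decides who has a second procedure and defines no comparison between arms.

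A reader might infer more than the documents support:
- **That the plan's false-positive rate is about 10%.** This needs an either-test rule, which the SAP does not contain.
- **That the SAP sentence allows power as low as 5%.** This needs baseline left out, the interaction used alone, and an effect exactly constant over the follow-up visits. It is an unlikely combination.
- **That no 6-month comparison can be as randomised.** If patients stay in their original arm, it is. The difficulty is then contamination by the other supplement.
- **That the exclusion creates false positives.** In the model above it weakens a real difference and gives no bias when there is none.

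**Conclusion.** The point holds in this form. It is certain from the text that neither document names the deciding ANOVA term or the levels of time, and that the protocol analyses 3-month non-improvers separately. The dilution to 0.75 under a constant effect is algebra. How many patients are lost, and how far the difference shrinks, rest on the assumed effect, improvement, correlation and definition of non-improvement. The 6-month range is model-specific, with greater shrinkage under AR(1) than under compound symmetry. This should be corrected, but it does not show that the plan's type I error exceeds 5%.

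**What to change.** Before unblinded results are seen, name one primary test in the SAP, for example:

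*Difference between randomised arms in [one named TMJ (intracapsular) pain VAS score], measured before any second procedure, in all randomised patients including those who later have one, adjusted for the baseline score, two-sided 5%, reported with its 95% confidence interval.*

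Use either the 3-month score or the mean of the 1- and 3-month scores, chosen in advance. Three months is the last scheduled visit before the alternative supplement is given. State how a missing score will be handled. Keep the ANOVA (both terms, with the levels of time stated) and the 6-month visit as secondary. The rule for the second procedure need not change.

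The cost is SAP wording and one matching phrase in the protocol; the pain scores are already collected. There are three downsides:
- An effect that appears only after 3 months would not count towards the primary result.
- At low correlation the 3-month contrast has less power than some ANOVA readings: 0.66 against 0.70 (group term with baseline) and 0.88 (group term on follow-ups only) at r = 0.3, under the assumed 30 per arm and 0.6 SD. The mean of 1 and 3 months recovers much of this unless the effect builds slowly.
- The documents do not show whether results have already been seen. If they have, the choice should be reported as made afterwards.

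Keeping both ANOVA terms at 0.025 each is a weaker remedy. It gives no single estimate, keeps the 6-month level, and can exceed 5% when the correlation between visits is not equal and no correction is made.

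### The SAP's only test is a two-way ANOVA with no missed-visit rule and no named primary effect; in standard form, one missed visit discards the patient's other pain scores.

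*SAP*

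**What the plan says.** The statistical plan is one paragraph. Besides descriptive statistics, the SAP (Statistical Analyses) names one inferential method, a "two way ANOVA, 1 between (treatment groups), 1 within (time"), "using a probability level of < 0.05". It adds: "The primary outcome variable will be intracapsular pain".

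The protocol places pain and clinical assessments "at 1 month, 3 months and 6 months when the pain VAS measures and a clinical exam will be assessed". It also refers to "standard pain and physical measures that are recorded before and after treatment", so there is a pre-treatment score. Time therefore has three levels, or four if baseline counts as one; the SAP does not say which.

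Neither document gives a rule for missed visits, dropout or imputation. Neither says whether the group main effect, the group-by-time effect or a comparison at one visit answers the efficacy question. The nearest related statement is in the protocol: patients whose pain has not improved at 3 months receive the other supplement and are analysed apart from those who complete six months. That concerns non-improvers, not missed visits.

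**The concern.** A split-plot ANOVA in its standard form works on complete rows. A patient who misses one follow-up visit is dropped, together with the three scores already collected (two if baseline is not a level of time). Scores that patients have provided are then unused. The comparison can also be biased if missingness relates to pain differently in the two arms.

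The SAP does not say whether incomplete rows are deleted, imputed or kept through a likelihood-based fit. With no primary effect named either, both choices could be made after the data are seen.

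The cost depends on the pattern of missed visits and on the contrast. It is clear when patients miss a visit and return, or when the contrast averages visits. It is close to nil for a 6-month contrast under permanent dropout, because no model recovers 6-month scores that were never recorded.

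**Working it through.** **Inputs from the documents.** Treatment is the between factor and time the within factor; significance level 0.05; follow-up at 1, 3 and 6 months; a pre-treatment score. Sample size, power, effect size, SD and dropout rate are not stated, so the plan has no figure to reproduce.

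**Assumed inputs.** Miss rate q = 5%, 10% or 15% per follow-up visit, baseline always observed. Correlation between visits is r^gap, with r = 0.6-0.9 per month and 0%, 25% or 50% of the variance being visit-level noise. The covariance of months 1, 3 and 6 is taken conditional on baseline and treated as known.

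**Step 1: patients lost.** For independent misses, or dropout with hazard q at each visit, the share lost is 1 - (1 - q)^3:
- q = 0.05: 1 - 0.857 = 14%
- q = 0.10: 1 - 0.729 = 27%
- q = 0.15: 1 - 0.614 = 39%

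If the same patients miss every visit, the share lost is q itself.

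**Step 2: collected follow-up scores discarded.** The share is 1 - 3(1 - q)^3 / (expected follow-up scores per patient).
- Independent misses: the denominator is 3(1 - q), so the share is 1 - (1 - q)^2 = 9.75%, 19.0%, 27.75%.
- Dropout with hazard q: the denominator is (1 - q) + (1 - q)^2 + (1 - q)^3. At q = 0.10 this is 2.439, and 1 - 2.187/2.439 = 10.3%. For the three rates: 5.1%, 10.3%, 15.7%.
- Same patients miss every visit: 0%.

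**Step 3: power after deletion.** Ratio = complete-row variance / all-available variance. With 80% power when all available visits are used, power after deletion = Phi(2.802/sqrt(ratio) - 1.960). Example: ratio 1.276 gives 2.802/1.1296 - 1.960 = 0.521, so power is 69.9%.

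| Pattern | Rate | 6-month ratio | Power | Three-visit average ratio | Power |
|---|---|---|---|---|---|
| Independent misses, per visit | 5% | 1.109-1.127 | 75-76% | 1.118-1.146 | about 75% |
| | 10% | 1.236-1.276 | 70-71% | 1.257-1.320 | 68-70% |
| | 15% | 1.386-1.451 | 64-66% | 1.423-1.531 | 62-65% |
| Dropout, hazard per visit | 5% | 1.001-1.022 | 79-80% | 1.057-1.067 | 77-78% |
| | 10% | 1.001-1.045 | 78-80% | 1.118-1.141 | about 75% |
| | 15% | 1.002-1.068 | 77-80% | 1.184-1.222 | 72-73% |
| Dropout, total by 6 months | 5% | at most 1.007 | at least 79.7% | at most 1.022 | at least 79.1% |
| | 10% | at most 1.015 | at least 79.4% | at most 1.046 | at least 78.2% |
| | 15% | at most 1.023 | at least 79.1% | at most 1.071 | at least 77.3% |
| Same patients miss every visit | 5-15% | 1.000 | 80% | 1.000 | 80% |

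**Step 4: bias illustration.** The simulation had 1,000,000 patients per arm and no true effect. In one arm, 5-15% dropped out after month 1 depending on 1-month pain (odds ratio 2-3 per SD); in the other, the same share dropped out at random. Complete-row bias was at most 0.026 SD at 6 months and 0.057 SD for the average. The all-available likelihood estimate was within 0.004 SD of zero.

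**Side note on sphericity.** The SAP states no correction. In a null simulation with four visits and an assumed 20 or 40 patients per arm, the uncorrected group-by-time test had size about 5.1-5.6% with 25-50% visit noise and up to about 7% with none. The group main effect is not affected.

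**The case against.** Four objections carry weight.

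- **Every rate is assumed.** This stands. The large losses need frequent intermittent misses, or dropout near 10-15% at every visit together with an averaged contrast. A reader might infer that the trial will lose 14-39% of its patients, or that its power will fall to the low 60s. The documents do not support either, since they give no sample size, miss rate or pattern.
- **The power figures are not for the SAP's own tests.** This also stands. The ANOVA gives an unadjusted group main effect and an omnibus group-by-time effect, and neither was evaluated. The three-visit average is the nearer analogue, because the group main effect compares averages over visits. The figures isolate the cost of deletion; they do not give the planned test's loss.
- **The SAP names factors, not a method of estimation.** The same design could be fitted as a mixed model that keeps every score. A reader might infer that the SAP mandates deletion; it does not. It is silent, and that silence is the gap. One sentence on incomplete rows and one naming the primary effect would close the minimum gap.
- **All available 6-month scores is undefined for crossover patients.** By then they have received both supplements. Including their 6-month scores and setting them aside are different analyses, and setting them aside makes missingness depend on 3-month pain. This stands and has to be settled in the fix. None of the figures above includes crossover.

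A reader might also infer serious bias or a badly inflated error rate. The illustrated bias is at most 0.06 SD, and the sphericity effect is small and confined to the within-patient tests.

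**Conclusion.** The concern holds in a limited form. The SAP should say how incomplete rows are handled and which effect is primary, and an all-available mixed model is a better primary analysis than a complete-row ANOVA.

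The gain depends on the missingness pattern: roughly 4 to 18 points of power for intermittent misses at 5-15% per visit, at most about 1 point at 6 months and 3 points for the average if 5-15% is total dropout, and none if the same patients miss every visit. Those figures rest on the assumed correlations and apply to baseline-adjusted contrasts. This is an inexpensive improvement worth making, not evidence that the planned comparison is invalid.

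**What to change.** Make the primary analysis a mixed model for repeated measures, fitted by REML to all available 1-, 3- and 6-month pain scores. Include baseline pain as a covariate, treatment, categorical visit and treatment-by-visit. Name one primary contrast and state the missing-at-random assumption. Unstructured covariance with Kenward-Roger degrees of freedom is a suitable default but not essential.

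In the same SAP text, reconcile this with the protocol's separate analysis of crossover patients. Keep their 1- and 3-month scores in the model under the randomised group, and state explicitly how their 6-month scores, recorded after the alternative supplement, are treated.

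If the ANOVA is kept, use it as a sensitivity analysis, state how incomplete rows are handled, and apply Greenhouse-Geisser to its within-patient tests.

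The cost is SAP wording, slightly more analysis work, a few more covariance parameters (six for three visits if unstructured) and reliance on missing at random. Under permanent dropout the power gain at 6 months is close to nil. No visit or procedure changes.
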